SMART Trial: Steroid Dosing by bioMARker
Guided Titration in Critically Ill Patients
With Pneumonia

NCT03852537

January 4, 2021

SMART trial: Steroid dosing by bioMARker guided Titration in critically ill patients with Pneumonia.

IRB number:-18-010925

Principal Investigator: [name] M.D

Co-Principal Investigator: [name] M.D.

Co-investigators: [name] M.D, [name] M.D, [name] Pharm.D.

Statistician: [name] M.S

Protocol Version: 8; 1/4/2021

Abstract

Pneumonia is the most common cause of acute hypoxemic respiratory failure. The limited and variable use of corticosteroids in critically ill patients with pneumonia is largely due to an inability to identify patients that will benefit from the use of anti-inflammatory medications. Increased levels of pro-inflammatory mediators are a prominent feature of pneumonia and previous studies have tracked the effect of steroids on inflammatory biomarkers or, more recently, used biomarkers (i.e. C Reactive Protein -CRP) to enroll patients in to clinical trials. The objective of this prospective, single-center pilot trial is to compare individualized, biomarker concordant vs usual care in patients with pneumonia and acute hypoxemic respiratory failure identified in the emergency department whose bedside physicians intend to provide adjunctive corticosteroid treatment. These data will be used to assess feasibility, refine the protocol, and calculate the sample size in preparation for a larger pragmatic clinical trial comparing the two strategies.

Research Plan

I. Specific Aims

Specific Aim 1: To assess the feasibility, safety and preliminary efficacy of individualized, biomarker-guided corticosteroid dosing compared to usual care in critically ill patients with community acquired pneumonia and acute hypoxic respiratory failure. We hypothesize that, compared to usual care; individualized, biomarker-guided corticosteroid dosing will lead to:

- Lower cumulative exposure to corticosteroids
- Lower incidence of adverse events (hyperglycemia, delirium, and nosocomial infections)
- Improvement in pulmonary organ function based on requirements for oxygen and advanced respiratory support
- Reduced hospital length of stay

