This pilot study is being conducted to assess the feasibility of recruiting patients and clinician adherence to steroid protocol, to refine the trial intervention and endpoints, and to calculate target sample sizes in preparation for a larger pragmatic clinical trial comparing the two approaches to corticosteroid administration.

Specific Aim 2: To evaluate the trajectories of C-reactive protein (CRP), pulmonary and non-pulmonary organ failures over time in patients from the two study arms.

In addition to assessing the feasibility of individualized, biomarker guided steroid dosing, this pilot study is necessary to evaluate the usefulness of CRP as a predictive enrichment tool in identifying patients in whom steroid administration will be most beneficial and also as a prognostic enrichment tool (alongside severity of pulmonary and other organ failures) to identify patients at higher risk of poor outcomes. It will inform the target population and will help refine the thresholds for initiation, titration and discontinuation of individualized corticosteroid therapy used to reduce inflammation in patients with pneumonia and acute hypoxic respiratory failure

Specific Aim 3: To evaluate the role of a biomarker-titrated adjuvant corticosteroid administration compared to usual care in patients admitted to hospital with SARS Co-V 2 (COVID-19) infection. We hypothesize that, compared to usual care, individualized biomarker-titrated dosing will be associated with:

- a) Improvement in pulmonary organ function based on requirements for oxygen and advanced respiratory support

- b) Reduced hospital length of stay
- c) Reduced cardiovascular complications including evidence of myocardial injury, need for inotropes and new/worsening arrhythmias

II. Background and Significance

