CRP/procalcitonin who were treated with steroids or patients with a low CRP/procalcitonin who were not treated with corticosteroids), versus treatment that was biomarker-discordant. The threshold for an elevated CRP was 150mg/L and the threshold for an elevated procalcitonin was 2.2ng/ml. After adjusting for severity of illness, early (within 12 hours of ICU admission) steroid administration in patients with pneumonia or ARDS was associated with decreased persistence or progression of pulmonary and other organ failures, reduced hospital and ICU length of stay and decreased hospital mortality(table 1). Patients with biomarker-concordant and biomarker-discordant corticosteroid treatment had similar baseline severity of illness. Biomarker-concordant corticosteroid treatment was associated with faster recovery of hypoxemia (table 2). No significant differences in mortality or hospital/ICU length of stay were seen between the biomarker-concordant versus the biomarker discordant group.

Table1. Impact of early corticosteroid use on outcomes in ICU patients with pneumonia and ARDS

	Steroids ≤ 12h after ICU admission (N=1047)	Steroids > 12h after ICU admission(N=567)	P value
SOFA Day 1	5 (3-8)	6 (4-8)	0.006
SOFA Day 2	4 (2-6)	5 (3-8)	<0.001
SOFA Day 3	4 (2-7)	5 (3-8)	0.009
PaO ₂ /FiO ₂ at ICU admission	173 (117-250)	161 (108-240)	0.16
PaO ₂ /FiO ₂ after 24h	196 (143-265)	183 (122-255)	0.03
PaO ₂ /FiO ₂ after 48h	209 (145-284)	191 (129-255)	0.03
ICU length of stay	1.98 (1.07-4.0)	3.69 (1.95-7.24)	<0.001
Hospital Length of stay	7.57 (4.55-14.07)	10.4 (6.08-20.8)	<0.001
ICU Mortality	102 (9.7%)	69 (12.2%)	0.15
Hospital Mortality	188 (17.9%)	132 (23.3%)	0.01

Table 2: Impact of steroid use that was concordant versus discordant with markers of inflammation on outcomes in critically ill patients with pneumonia

	Biomarker Concordant (N=130)	Biomarker Discordant(N=114)	P value
FIO ₂ at ICU admission	40 (30, 60)	40 (30, 60)	0.47
FIO ₂ Day 2	35 (28, 50)	40 (31, 50)	0.07
FIO ₂ Day 3	31 (21, 40)	37 (29, 50)	0.004
FIO ₂ Day 4	28.0 (21.0, 37.5)	35 (28, 50)	<.001
FIO ₂ Day 5	28 (21, 36)	28 (24, 45)	0.03
ICU free days (Median estimate (95%CI)	1.97 (-0.50, 4.45)	0.00 (Ref)	0.12
Hospital free days (Median estimate (95%CI)	1.79 (-0.98, 4.57)	0.00 (Ref)	0.21
ICU Mortality (Hazard Ratio with 95% CI)	0.93 (0.31, 2.74)	1.00 (Ref)	0.89
Hospital Mortality (Hazard Ratio with 95% CI)	0.75 (0.36, 1.59)	1.00 (Ref)	0.45
Delirium	36 (27.7%)	34 (29.8%)	0.71

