In the individualized, biomarker-concordant arm, all patients will receive steroids once at the time of admission, then a daily morning dose. In order to account for varying turnaround time at different laboratories, CRP levels will be drawn with early morning labs, and used to determine the steroid dosing for the day. Patients will receive daily CRP measurements for the first 5 days of the hospitalization, or until hospital discharge. Steroid administration will be facilitated using standardized computerized physician order entry. Steroid order sets will include 6 hourly point of care glucose monitoring, and an insulin sliding scale for glucose levels to facilitate glucose management. The need for insulin drip will be determined by the treating physician. Additional testing including serum and urine ketones will be informed by the glucose level, serum anion gap and bicarbonate levels in routine basic metabolic panels and determined by the treating physician. Glucose levels, new or worsening infections within 30 days of start of steroid (positive blood/sputum/urine culture) and Confusion Assessment Method in the ICU will be documented in case report forms.

In the usual care arm, patients will receive daily CRP measurements for the first 5 days of the hospitalization, or until hospital discharge. However, these CRP measurements will not be accessible to the treating physicians.

An oxygen titration protocol will be utilized to standardize oxygen weaning in both arms (please see appendix).

Daily Troponin measurements will be added in both arms

Primary outcomes:

- Feasibility: a percentage of eligible patients adhered to the timely initiation and daily treatment according to ESICM/SCCM clinical practice guideline (control group) or biomarker concordance (intervention group)

Secondary outcomes

- Death
- Progression of disease as defined by the need for high flow nasal cannula oxygen, noninvasive or invasive ventilation. Given the proliferation of high flow nasal cannula oxygen use in lieu of mechanical ventilation, instead of ventilator-free days we opt for

using advanced respiratory support free days where “advanced respiratory support” includes both invasive and noninvasive mechanical ventilation and the high flow nasal cannula oxygen.

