- Evolution of respiratory and other organ failures measured by SOFA at time of ICU admission, after 24 hours, after 48 hours and after 72 hours and by the organ failure free days. In the absence of daily arterial blood gas analysis, for respiratory component of SOFA, $\text{PaO}_2/\text{FiO}_2$ ratio will be replaced by $\text{SpO}_2/\text{FiO}_2$ ratio
- Need and duration of vasopressors and inotropes use (based on cardiovascular SOFA sub-score)
- New onset/worsening arrhythmias
- Evidence of myocardial injury determined by daily troponin peak and/or new diagnosis of LV dysfunction ($\text{LVEF} < 40\%$) or new diagnosis of cor pulmonale (\geq moderate RV dysfunction)
- Re-hospitalization for a primary cardiovascular diagnosis within 30 days
- Side effects of steroid (Safety) including
 - Hyperglycemia and its complications- Diabetic ketoacidosis (DKA) and Hyperosmolar hyperglycemic syndrome (HHS), the need for insulin
 - Delirium (measured by CAM-ICU) and
 - New infections in patients with pneumonia and/or ARDS
- Length of ICU and hospital stay
- Time to discontinue oxygen or return to baseline oxygen use
- Requirement and duration of non-invasive and invasive mechanical ventilation
- ICU, and 30, 60 and 90-day mortality
- Discharge, 30, 60, and 90-day disposition (home vs other)

C. Sample Size and Power: In this pilot study, we do not have the power to test the efficacy of the intervention on patient-centered outcomes. However, this pilot data will provide us with potential effect size data necessary for sample size determination for the future phase II/III study.

D. Data Collection: Case Report Forms will be completed by research coordinators and entered in a REDCap database.

E. Data Handling:

- Protected health information will be preserved by having patient data be de-identified and given a study number.
- This data will be recorded using REDCap and JMP. Any written data will be stored in storage files in a locked access building.
- Data will only be accessible to investigators/participating personnel.
- The computers where the data will be stored meet strict security requirements imposed by Mayo Clinic.
- No data containing PHI will be transported on data sticks or laptops without being encrypted or password protected.
- No hardcopy information containing PHI will be transported/removed from the Mayo campus.
- Any hard copies of archival source documentation will be stored in a locked, secure location only accessible to the study personnel.

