- No data will be disclosed to another institution and all identifiers linking to the patient will be destroyed after data collection is complete.

f. Data Analysis

Aims 1 and 3: Continuous outcomes will be compared between treatment arms using linear regression and binary outcomes using chi-square or fishers exact tests. Secondary outcomes will be tested without adjustment for multiple comparisons. Data from this study, including estimated effects of the intervention and sample variation in outcomes, will provide valuable information to plan a well-powered subsequent phase II trial.

Aim 2: The correlation between CRP levels and corticosteroid dosing in those who receive individual-dose steroids versus usual care will be examined using Pearson's correlation coefficient. The effect of CRP levels on the secondary outcomes will be evaluated using multivariable analysis adjusting for severity of illness. The data from this study will help evaluate the usefulness of CRP as a predictive and prognostic enrichment tool and thus help inform and refine the thresholds for initiation, titration and discontinuation of corticosteroids in the subsequent larger study.

Decision to proceed with a larger study: The decision to proceed with a phase II/III study will be based on the following criteria:

- Ability to enroll an adequate number of eligible patients early in the course of illness. The expected hurdles include delayed identification of potentially eligible patients, provider/patient refusal, non-adherence to protocol, and inability to obtain CRP levels in a timely manner.
- Safety; i.e. absence of significant adverse events.

- Preliminary efficacy: ability to show reduction in steroid use, reduced episodes of hyperglycemia and favorable trajectory of pulmonary organ dysfunction.

The data collected will be essential to adequately plan the future study, estimate power and sample size, refine exclusion/inclusion criteria and determine the number and characteristics of future study sites.

g. Feasibility and Time Frame:

We believe that our project is feasible in the time frame of the grant; we hope to use the preliminary data generated from this pilot study to decide about moving forward with a phase II/III study involving a larger study group and more centers (Table 5).

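### Hospital stay, hypothesised to fall in Aims 1 and 3, has no rule for in-hospital death, so the stay effect is mixed with mortality and can point the wrong way

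*Combined protocol and SAP*

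**What the plan says.** Section I, Aim 1 lists "Reduced hospital length of stay" among the expected effects of biomarker-guided dosing, and Aim 3 repeats it for COVID-19 as hypothesis "b) Reduced hospital length of stay". Section IV.B gives the matching secondary outcome as "Length of ICU and hospital stay", with no time window, survivor restriction or rule for death. Section IV.f states: "Continuous outcomes will be compared between treatment arms using linear regression".

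Free-days measures appear in three other places.
- Section IV.B replaces ventilator-free days with a broader measure ("using advanced respiratory support free days where" the term covers invasive and noninvasive ventilation and high-flow nasal oxygen).
- Section IV.B follows organ failure by SOFA and also "by the organ failure free days".
- Section III, Table 2 reports stay in the team's own cohort as ICU free days and "Hospital free days (Median estimate (95%CI").

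None of these places states a window or a score for patients who die. Death, and mortality in the ICU and at 30, 60 and 90 days, are separate secondary outcomes. The durations of ventilation and of vasopressor and inotrope use are also listed.

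**The concern.** A patient who dies on day 3 has a 3-day stay. In a regression of stay on arm, that counts as a better result than recovery and discharge on day 10. The arm difference then combines how fast survivors go home, how many patients die, and when they die. A treatment that changed only mortality would show an effect on stay, and its direction would depend on the timing of the deaths. The same applies to a raw duration of ventilation or vasopressor use.

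Two things are at stake. One is the reading of a hypothesis named in two aims. The other is the planning of the larger trial, because Sections IV.C, IV.f and IV.h say that effect sizes and outcome variation from this pilot will be used for that.

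**Working it through.** **Mortality (Section III, Table 1).** Hospital deaths are 188/1047 = 17.96% (printed as 17.9%) and 132/567 = 23.28%. An uncorrected chi-square test gives P = 0.010, which reproduces the printed 0.01. Pooled: 320/1614 = 19.8%.

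**Expected deaths in 44 patients.** 44 × 0.198 = 8.7. As a range: 44 × 0.10 = 4.4 to 44 × 0.30 = 13.2.

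**Direction of the bias.** Let *m* be hospital mortality, *s* the mean stay of survivors and *d* the mean day of in-hospital death, with *s* and *d* equal in both arms.
- Mean raw stay = (1 − m)s + md, so the arm difference is (m₁ − m₀)(d − s). Its sign turns at d = s.
- Hospital-free days to day 28, with death scored 0 and all survivors staying *s* days, are (1 − m)(28 − s). The arm difference is −(m₁ − m₀)(28 − s), whatever the value of *d*.

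Assumptions: m₀ = 20%, m₁ = 30%, unchanged recovery.
- Formula: s = 10, so raw stay changes by 0.1 × (d − 10) and hospital-free days by −0.1 × 18 = −1.8.
- Simulation: survivor stay is lognormal, matched to Table 1's early-steroid column, "7.57 (4.55-14.07"), taken as days. That gives σ = (ln 14.07 − ln 4.55)/(2 × 0.67449) = 0.837 and a mean of 10.7 days. Time to death is gamma with shape 2.

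| Mean day of death | Raw stay, formula | Raw stay, simulation | Hospital-free days, simulation |
|---|---|---|---|
| 3 | −0.7 | −0.76 | −1.81 |
| 5 | −0.5 | −0.58 | −1.81 |
| 8 | −0.2 | −0.27 | −1.81 |
| 11 | +0.1 | +0.02 | −1.81 |
| 15 | +0.5 | +0.42 | −1.80 |
| 20 | +1.0 | +0.91 | −1.80 |

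Entries are days, higher-mortality arm minus the other. The crossover is about day 10 to 11. A lognormal fitted to Table 1's later-steroid column, 10.4 (6.08–20.8), has a mean of 15.8 days, which would move the crossover to about day 16.

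The bias runs both ways. If mortality falls from 20% to 10%, raw stay lengthens by 0.77, 0.57 and 0.29 days for deaths at day 3, 5 and 8. Comparing medians of raw stay does not cure it: for the rise to 30% the median shifts by −0.71, −0.42 and −0.09 days.

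**At trial size (22 per arm, assuming 1:1; the ratio is not stated).** For mean death day 3, 5 and 8, raw mean stay favours the arm with the higher true mortality in 61%, 58% and 54% of simulated trials. Hospital-free days do so in 28%, 27% and 28%.

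**Against noise.** Table 1's quartiles imply an SD of about 7.1 days (normal: 9.52/1.349) to 10.8 (lognormal). The standard error of a difference is SD × √(2/22), about 2.1 to 3.3 days.

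**The case against.** The strongest objection is that the plan leaves a rule unstated and does not define a wrong one. A reader might infer that the documents fix the outcome as raw stay, so that early deaths certainly count as short. They do not quite say that. The text of Section III reports no significant difference in length of stay between the concordant and discordant groups, yet the only stay rows in Table 2 are free days. The team has therefore used the phrase for a free-days measure. Table 1 uses it for what look like plain stays. Raw stay remains the likely reading, but not the only one.

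A reader might also infer that Table 2 scores deaths as zero, or that the other free-days outcomes already settle the matter. No window or death score is given anywhere, so neither follows.

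Four further points stand.
- Mortality is reported separately, so a short stay would be seen beside the deaths.
- Section IV.C claims no power for patient-centred outcomes, and stay is not among the criteria for proceeding in Section IV.f.
- The respiratory-support and organ-failure free-days outcomes partly cover ventilation and vasopressor duration.
- The illustrated bias of 0.2 to 0.8 days is small beside a standard error of 2 to 3 days.

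None of this repairs the stay estimate itself. A separate mortality row does not remove deaths from the stay comparison, and with about 9 deaths a mortality difference would be imprecise. Random error is allowed for when a pilot estimate is carried forward with its interval, whereas a bias of unknown sign is not.

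**Conclusion.** The point holds in a limited form. Stay is hypothesised to improve in two aims and has no rule for in-hospital death. On the plain reading its arm difference mixes recovery with mortality. It can point the wrong way if deaths come, on average, before the average survivor's discharge: about day 10 to 11 under the assumptions above, and later if survivors stay longer.

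The sizes rest on an assumed 10-point mortality difference, unchanged recovery, assumed times of death, and a Table 1 stay distribution applied to survivors although the table does not say it excludes deaths. The 19.8% comes from a retrospective ICU cohort. The trial enrols on an oxygenation criterion and excludes refractory septic shock and comfort care, so its mortality may differ.

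A reader might go further and conclude that the trial would pass off a harmful strategy as beneficial. The documents do not support that. They give no timing of deaths, deaths are reported, and stay does not enter the decision to proceed. What is affected is the stay result and the stay effect size and variance taken into the next trial. The plan should be changed, but the point does not threaten the pilot's feasibility purpose.

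**What to change.** - Make the efficacy comparison ICU-free and hospital-free days to a stated day, for example 28. State that death within the window scores 0 and how readmission counts. Reword the two hypotheses to match. Time to discharge alive, with death as a competing event, is an acceptable alternative.
- Free days are bounded and have a block of zeros, so use a rank-based or median comparison in place of linear regression or beside it. Table 2 already reports median estimates.
- Report raw stay, ventilation duration and vasopressor duration descriptively, by survival status. For between-arm comparison rely on the free-days outcomes already listed for respiratory support and organ failure, with the same explicit window and death rule.

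The cost is small. Stay and 30-day mortality are already outcomes, so admission, discharge and death dates should be on hand. Only cardiovascular re-hospitalisation is listed, so a rule that counts any readmission would need those dates added. Free days are slightly less direct to interpret than days in hospital, and a little more analysis is needed.

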Hyperglycemia	30 (23.8%)	26 (23.4%)	0.94

[figure not shown]
Team experience: [name] is an Assistant Professor and Senior Associate Consultant in the Division of Pulmonary and Critical Care at the Mayo Clinic. He has expertise in ARDS epidemiology research and the incorporation of biomarkers in ARDS risk prediction. [name] is a clinical fellow in Critical Care at Mayo Clinic, Rochester with an interest in critical care outcomes research. [name] is a research trainee at Mayo Clinic, Rochester also with an interest in critical care outcomes research. [name] is an assistant professor and clinical pharmacist at Mayo Clinic, Rochester with an interest in individualizing pharmacotherapy for critically ill patients with infections. [name] is an internationally renowned leader in ARDS research and founder of our multidisciplinary clinical research laboratory (METRIC), and Director of Critical Care Research at Mayo. Within this group, we have adequate resources, expertise and training to achieve our scientific objectives.

IV. Research Design and Methods

Figure 1 summarizes study design. A two-arm multicenter randomized trial

Hospital presentation:
Emergency Department

Adult Patient with Pneumonia + Acute Hypoxic Respiratory Failure

A. Study Design or Overview

Specific Aims 1 and 3: We plan to perform a two arm multi-center pilot phase II clinical trial. 44 patients with pneumonia (additional strata to include patients with COVID-19 for specific aim 3) and acute respiratory failure defined by $\text{SpO}_2/\text{FiO}_2 < 315$ ($\text{SpO}_2 < 90\%$ on room air or $< 97\%$ on 2L/min O_2) will be included.

- Control arm: Usual care
- Intervention arm: individualized, biomarker concordant steroid use: dosing, titration and duration according to CRP level (Table 3).

Table 3. Biomarker-concordant steroid treatment

CRP (mmol/L)	Methylprednisolone (daily)
<50	None
51 - 100	0.5 mg/kg
101 - 150	0.75 mg/kg
151 - 200	1 mg/kg
>200	1.5 mg/kg

*per ideal body weight

Randomization will be stratified based on the need for high flow nasal cannula oxygen, noninvasive or invasive ventilator support.

Definitions

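### Randomisation is stratified on respiratory support, but the arm comparisons for Aims 1 and 3 leave the stratum out (minor, almost free to correct)

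*Combined protocol and SAP*

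**What the plan says.** Section IV.A (Study Design or Overview): "Randomization will be stratified based on the need for high flow nasal cannula oxygen, noninvasive or invasive ventilator support". The same section mentions additional strata for patients with COVID-19, without saying clearly whether these are randomisation strata. Figure 1 is not in the text supplied, so the number of levels and the blocking method are unknown here and are not held against the plan.

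Section f (Data Analysis), on the comparison of arms for Aims 1 and 3, states: "Continuous outcomes will be compared between treatment arms using linear regression and binary outcomes using chi-square or fishers exact tests". No covariate or stratum is mentioned. The Aim 2 paragraph of the same section does name an adjustment, for severity of illness, but for the effect of CRP and not for the comparison of arms.

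Section C (Sample Size and Power) disclaims power for efficacy, but adds that "this pilot data will provide us with potential effect size data necessary for sample size determination for the future phase II/III study". Section f likewise intends to plan the next trial from the estimated effects and the spread of the outcomes.

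**The concern.** Stratifying makes the arms alike on respiratory support. If support also predicts outcome, that balance removes a source of variation from the difference between arms. An analysis without the stratum still charges that variation to the error term, so its standard error describes a noisier design than the one that was run.

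The two outcome types differ. Linear regression can carry a stratum term, so for continuous outcomes the model is merely unspecified. The chi-square and Fisher tests, as named, have no place for a stratum.

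At stake is precision in a trial of 44 patients, and the quality of what it hands on. A marginal SD mixes supported and unsupported patients. A later trial that adjusts for support would want the within-stratum SD.

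**Working it through.** **Is there a figure to reproduce?** No. The 44 patients follow from coordinator availability over two years (section i, Limitation). The plan states no power, alpha, effect size, event rate or allocation ratio.

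**Inputs.** From the plan: 44 patients, stratified randomisation, the named tests. Assumed: 22 per arm, two-sided 5%, two strata with arms balanced within them (11 and 11 per arm unless stated), and all risks and variance shares.

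**Binary outcomes, approximate reason.** Chi-square uses the variance p̄(1 − p̄), with p̄ the overall risk. With balanced strata the true variance is the mean of p(1 − p) over strata. The standard error is therefore too wide by k = √[p̄(1 − p̄) / mean of p(1 − p)], and type I error is about 2Φ(−1.96k).

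- Risks 40/20%: k = √(0.21/0.20) = 1.025, type I error 4.5%.
- Risks 60/20%: k = √(0.24/0.20) = 1.095, type I error 3.2%.
- Risks 80/20%: k = √(0.25/0.16) = 1.25, type I error 1.4%.

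**Binary outcomes, exact enumeration** of the four binomials (Pearson chi-square and CMH without continuity correction, two-sided Fisher). Power is at a common within-stratum odds ratio of 0.15.

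| Stratum risks | Type I: chi-square | Fisher | CMH | Power: chi-square | CMH |
|---|---|---|---|---|---|
| 30/30% | 4.8% | 2.4% | 4.9% | 58% | 58% |
| 40/20% | 4.3% | 2.1% | 5.0% | 57% | 57% |
| 50/20% | 3.6% | 1.6% | 4.9% | 61% | 63% |
| 60/20% | 2.9% | 1.2% | 5.0% | 63% | 67% |
| 80/20% | 1.4% | 0.5% | 5.2% | 53% | 68% |

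Fisher is already at 2.4% with no stratum effect, so only the fall below that is due to ignoring the stratum. With 6 supported and 16 unsupported per arm, the CMH gain in power over chi-square is 0, 0, 1, 3 and 12 points down the rows.

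**Continuous outcomes.** Let R² be the share of variance explained by the stratum and σ the within-stratum SD. Under exact balance the expected residual variance is σ²[1 + (44/42) × R²/(1 − R²)] without the stratum term and σ² with it. The ratio of standard errors is the square root of the bracket.

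| R² | SE ratio | Type I, unadjusted: exact balance | blocks of 4 | no within-stratum balance |
|---|---|---|---|---|
| 10% | 1.06 | 4.0% | 3.9% | 5.0% |
| 20% | 1.12 | 2.9% | 3.1% | 4.9% |
| 30% | 1.20 | 2.1% | 2.0% | 5.1% |
| 40% | 1.30 | 1.0% | 1.4% | 5.0% |

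The type I errors come from 20,000 simulated trials per setting. With the stratum term they were 4.8 to 5.2% throughout, and bias was at most 0.005 SD. Power for a difference of 0.8 within-stratum SD, exact balance, over the four rows: unadjusted 70/65/59/51%, adjusted 73/74/73/74%.

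**The case against.** The case for leaving the plan alone is fair on size. The primary outcome is feasibility, efficacy power is disclaimed, and no stated power claim is undermined. Every input above is assumed, and an odds ratio of 0.15 is extreme. Even there, CMH gains 0 to 2 points over chi-square up to risks of 50/20%. At an odds ratio of 0.5 and 60/20%, power is 12.0% for chi-square and 16.5% for CMH, too low to matter in a pilot. Support need not predict every binary outcome: death is plausible, hyperglycaemia or culture-positive infection less so. All of this stands and limits the weight of the point. It does not remove it, because the pilot's estimates are meant for planning and the correction is a matter of wording.

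A reader might go further on the outcome "Progression of disease as defined by the need for high flow nasal cannula oxygen, noninvasive or invasive ventilation", which uses the supports that define the strata but states no baseline or window. No listed exclusion removes patients already supported. Read literally, they would be events in both arms, and the risk difference would shrink by the factor (1 − s), where s is the share supported at randomisation. An assumed 40% against 20% among unsupported patients would give 20 × 0.75 = 15 points at s = 25% and 20 × 0.5 = 10 points at s = 50%.

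The documents do not support that as a finding. Worsening from the entry state is the ordinary sense of progression. The same bullet opts for "using advanced respiratory support free days", which may be its actual measure. The share s is not given. The shrinkage also lies inside the pilot's own 95% half-width, 1.96 × √(0.24/22 + 0.16/22) = 26 points. Progression is not named as a sizing endpoint or as a criterion for proceeding. What remains is a request for clarification: neighbouring outcomes do carry a reference ("Time to discontinue oxygen or return to baseline oxygen use"; "New onset/worsening arrhythmias"), while this one and "Requirement and duration of non-invasive and invasive mechanical ventilation" do not.

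**Conclusion.** The point holds as a minor improvement: the arm comparisons for Aims 1 and 3 should use the factor on which patients are randomised. For binary outcomes the named tests cannot do so; for continuous outcomes the model is silent.

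The consequence is conservatism and lost precision, and only if support is prognostic and the randomisation achieves balance within strata. Without that balance, type I error stays near 5% and adjustment only gains precision. If the stratum is not prognostic, nothing is lost. The power gain over chi-square becomes material only when the stratum is strongly prognostic: 4 points at 60/20% and 15 points at 80/20%, with equal strata and an odds ratio of 0.15.

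A reader might infer that the planned tests are invalid or that the effect estimates are biased. Neither follows: there is no excess of false positives and no bias in mean differences. The figures illustrate the mechanism and do not demonstrate an effect in this trial.

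**What to change.** In section f, before analysis:

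- Include the respiratory-support factor, as used in the randomisation, as a covariate in the linear regressions.
- For binary outcomes, use a CMH test without continuity correction, and an exact stratified test when events are few.
- If the factor has more than two levels and cells are sparse, collapse it to any versus no advanced support.
- If COVID-19 status was also a randomisation stratum, add it as a main effect in the regressions. Cross it in the binary tests only if counts allow: two equal strata leave 44/4 = 11 patients per arm and stratum, and crossing with COVID-19 leaves about 5.5.
- Report within-stratum and marginal SDs for planning.

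The cost is a few sentences and about one degree of freedom per two-level factor. The exact stratified test can lose a few points of power against Fisher when the stratum is weakly prognostic (32% against 36% with 6 and 16 per arm, risks 40/20%, odds ratio 0.15).

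As a separate clarification under Secondary outcomes, state whether progression means new or increased support relative to randomisation, or is measured by support-free days, and over what window.
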